5.8 Prior and Concomitant Therapy

Subjects receiving ergocalciferol or cholecalciferol must be taking $\leq 1,700$ IU/day and must remain on that same dose during the study.

Subjects receiving prior therapy with pharmacological doses ($>1,700$ IU/day) of ergocalciferol or cholecalciferol must be willing to discontinue or reduce the dose to $\leq 1,700$ IU/day and agree to remain on a stable dose during the study.

Subjects receiving other vitamin D analogs and/or bone metabolism therapy that could interfere with study endpoints must be willing and able to discontinue such therapy for the duration of the study. This includes doses of vitamin D analogs (eg, Rocaltrol[®], Zemplar[®], Hectorol[®], calcitriol), calcimimetics (Sensipar[®], Pasabiv[®]), teriparatide (Forteo[®]), calcitonin, bisphosphonates, denosumab (Prolia[®], Xgeva[®]) and other drugs that may affect calcium metabolism.

All concomitant medication usage from the 28 days prior to visit 1 until completion of the study will be recorded.

5.8.1 *Phosphate Binder and Elemental Calcium Therapy*

Use of calcium-based phosphate binder or antacid therapy such as calcium carbonate or calcium acetate (PhosLo[®]), are allowed up to 1000 mg/day of elemental calcium. Calcium-based phosphate binder or antacid therapy in excess of 1000 mg/day of elemental calcium should be discontinued or reduced for the duration of the study. Non-calcium based phosphate binder therapy such as sevelamer HCL (Renagel[®]) or lanthanum carbonate (Fosrenol[®]), and non-calcium based antacids can be used at the discretion of the investigator during the treatment and FU periods. Phosphate binder and calcium therapy should remain constant throughout the study. Any changes should be captured in the eCRF on the Phosphate Binder/Calcium Therapy page.

5.9 Restrictions

5.9.1 *Dietary Restrictions*

There are no study specific dietary restrictions. Subjects should follow their dietary plan if one has been prescribed. Any changes in prescribed dietary phosphorus or calcium therapy during the study should be captured in the eCRF.

5.9.2 *Subject Activity Restrictions*

Subjects should maintain their usual pattern of sun exposures (including use of tanning beds) and activities.

5.10 Treatment Compliance

During certain study visits, the study coordinator or designee will perform drug accountability and dosing compliance calculations (number of capsules that should have been taken versus actual number taken as evidenced by number of returned capsules). Dosing compliance at less than 80% should be reported as a protocol deviation.

5.11 Packaging and Labeling

Study drug will be provided in white, round, wide-mouth, HDPE bottles with 28-mm white, polypropylene, child-resistant (push down and turn) caps with aluminum heat induction seal liners and contain 30 capsules per bottle. Each bottle will contain either active drug or a matching placebo.

Study drug labels will include protocol number, name and address of the sponsor, investigational statement, storage conditions and instructions for use. Bottles will be assigned numbers that are linked to the randomization schedule through IRS to provide each subject with the appropriate dose per the schedule and the instructions of the IRS.

Do **NOT** dispense the bottle of capsules if the seal of the primary package appears compromised.

The subject will be instructed as follows:

NOT to take the drug if the product appears discolored or damaged upon visual inspection and to **NOTIFY** the site immediately of the condition of the study drug and the need to obtain replacement.

5.12 Storage and Accountability

CTAP101 Capsules will be shipped to sites following standardized shipment and temperature monitoring procedures.

While at the study site, CTAP101 Capsules will be stored at room temperature, 15-30°C (59-86°F) in the supplied packaging, with access granted to authorized personnel only.

All sites must ensure that study drug has been kept under required conditions prior to dispensing. A temperature log recording the daily storage temperatures will be maintained at each site for study drug. Accountability for study drug, from receipt until final reconciliation and return of drug by the monitor or designee, will be the responsibility of the investigator or the assigned designee(s).

In the case of temperature excursions, products should not be dispensed and the investigator or the assigned designee(s) should contact the clinical monitor or the sponsor representative as soon as possible to receive further instructions.

The investigator or assigned designee(s), will maintain study drug accountability records for study drug throughout the course of the study. Specifically, the investigator or assigned designee will confirm that all study drug supplies are received intact and in the correct amounts per the shipping forms. This will be documented by signing and dating the shipping forms and providing a copy to the sponsor or designee. A study drug accountability and dispensing log will record the study drug disposition, including dates, quantity of drug received, to whom dispensed (participant-by-participant accounting), and accounts of any drug accidentally destroyed. The site's running inventory of study drug supplies will be verified routinely throughout the course of the study. All opened and unopened containers of CTAP101 Capsules bottles are to be retained at the site until the sponsor or designee has performed a complete verification of the dispensation, following which study drug will be returned to the sponsor or designee.

5.13 Investigational Product Retention at Study Site

At the conclusion of the study, a final inventory will be performed by the investigator (or designee) and verified by the study monitor. Any discrepancies identified will be indicated, with a specific explanation of each discrepancy. The investigator (or designee) must return all unused medication in accordance with the sponsor's instructions, and a copy of the clinical supplies return documentation will be returned to the sponsor or designee. Drug accountability records, clinical drug supply receipts, and returns must be maintained by the investigator.

6 STUDY PROCEDURES

6.1 Informed Consent

A signed informed consent will be obtained from the subject's parent or legally appointed guardian prior to any study related procedures. The subject or their legally acceptable representative will be permitted time and opportunity to inquire about details of the study and to decide whether or not to participate. The subject or their legally acceptable representative will receive a copy of the signed and dated consent form and any written information provided to the study subjects. If any material change occurs that affects the conduct of the study, the subject will be required to sign an updated consent form.

The investigator or his/her designee will explain the nature of all aspects of the study to the subject, answer all questions regarding this study, and emphasize that missing data and premature termination of study participation will diminish the scientific value of the data obtained, prior to obtaining informed consent.

The process for obtaining subject informed consent will be in accordance with all applicable regulatory requirements. The subject or legally acceptable representative and the investigator or his/her designee must both sign and date the ICF before the subject can participate in the study. The original ICF will be retained in the site study records. The investigator or his/her designee will ensure documentation of the consent discussion in the subject's medical record/source document. The decision by the subject to participate in the study is entirely voluntary. The investigator or designee must emphasize to the subject that consent regarding study participation may be withdrawn at any time without penalty or loss of benefits to which the subject is otherwise entitled.

If the ICF is amended during the study, the investigator must follow all applicable regulatory requirements pertaining to approval of the amended ICF by the Institutional Review Board (IRB) and use of the amended form (including for ongoing subjects).

6.2 Medical History

A detailed medical history will be recorded at visit 1. The PE which is outlined in the following [Table 1](#) Evaluations will be performed by a licensed physician or by another suitably-qualified person where permitted by local regulations.

6.3 Physical Examination, Vital Signs, Body Mass Index, Body Weight and Height, 12-Lead Electrocardiogram, and Patient-Reported Palatability and Acceptability Assessments

Table 1. Evaluations

Physical Examination (PE):	
Organized by body system (excluding a urogenital examination) at visits 1, 3 and 28/ET
Vital Signs (VS) Measurements:	
Scheduled pulse, respirations and blood pressure will be measured prior to any scheduled blood draws and after the subject has been sitting for at least two minutesBody temperature (oral) in degrees CelsiusVS are measured at all visits
Body Weight and Height:	
Height will be recorded to the nearest 1 cm at visits 1, 3 and 28/ET.Body weight will be recorded to the nearest 0.1 kg at visits 1, 3 and 28/ET
Body Mass Index (BMI):	
Defined as the subject's weight in kilograms divided by the square of the subject's height in meters (kg/m^2). This is a derived variable and recorded at PE visits 1, 3 and 28/ET.
eGFR	
This is a derived variable based in the Modification of Diet in Renal Disease equation. Visit 1 creatinine value to be used for eGFR calculation.
12-Lead Electrocardiogram (ECG):	
Each 12-lead ECG will be started after the subject has been in the supine position for at least five minutesThe original ECG tracings, with global interpretation and signature of qualified medical personnel will be retained in the subject's records at the study site. Global interpretation categories are: Normal ECG, Abnormal ECG – not clinically significant, Abnormal ECG – clinically significant12-lead ECG will be performed once during visits 3 and 28/ETFor consistency of ECG data, every effort will be made to utilize the same facility and reader for all ECGs at each site
Patient-Reported Palatability and Acceptability Assessments	
Patient-reported palatability and acceptability assessments will be performed at Visits 13 and 22 in accordance with the Schedule of Events (see APPENDIX 1). Age-appropriate assessments will be used based on already-established and standardized versions of the combined hedonic facial and 10 cm visual analog scale. Site staff will be trained to give standardized, age-appropriate, brief and clear instructions to the subjects or, where appropriate, to the parents/guardians.

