4 STUDY POPULATION SELECTION

4.1 Study Population

The target population for this study is subjects having ages of 8 to <18 years who have been diagnosed with stage 3 or 4 CKD (as demonstrated by medical history and by an eGFR of ≥ 15 and <60 mL/min/1.73m² at screening) who do not require regular hemodialysis, and present with both VDI (serum total 25-hydroxyvitamin D <30 ng/mL) and SHPT (plasma iPTH >100 pg/mL for stage 3 CKD and >160 pg/mL for stage 4 CKD).

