4.2 Inclusion Criteria

Each subject must meet the following criteria to be enrolled in this study:

1. Cohort 1: Be 12 to <18 years of age and have a body weight of ≥ 40 kg; Cohort 2: be 8 to <12 years of age and have a body weight of ≥ 20 kg.
2. Be diagnosed with stage 3 to 4 CKD at least six months prior to the screening visit, and have an eGFR of ≥ 15 to <60 mL/min/1.73m² at screening.
3. Be without any disease state or physical condition that might impair evaluation of safety or which, in the investigator's opinion, would interfere with study participation, including:
 - a. Serum albumin ≤ 3.0 g/dL;
 - b. Serum transaminase (ALT or SGPT, AST or SGOT) > 2.5 times the upper limit of normal at screening; and,
 - c. Urinary albumin excretion of >3000 mcg/mg creatinine.
4. Exhibit during the initial or, if necessary, a screening visit after washout:
 - a. Plasma iPTH >100 pg/mL (stage 3 CKD) or >160 pg/mL (stage 4 CKD)
 - b. Serum calcium <9.8 mg/dL (corrected for albumin);
 - c. Serum total 25-hydroxyvitamin D <30 ng/mL; and,
 - d. Serum phosphorus >2.5 to ≤ 5.5 mg/dL (12 to <18 years) or ≤ 6.0 mg/dL (ages 8 to <12 years);
5. If taking calcitriol or other 1 α -hydroxylated vitamin D analogs, or cinacalcet, be willing to forgo treatment with these agents for the duration of the study and complete an 8-week washout period prior to commencing treatment in the study.
6. If taking $>1,000$ mg/day of elemental calcium, discontinue or reduce calcium use and/or use non-calcium based therapies for the duration of the study.
7. If receiving $\leq 1,700$ IU/day nutritional vitamin D (ergocalciferol or cholecalciferol) therapy, must agree to remain on a stable dose during the study.
8. If taking $>1,700$ IU/day of nutritional vitamin D, must discontinue or decrease the dose to $\leq 1,700$ IU/day, maintain that dose for the duration of the study, and complete an 8-week washout period prior to commencing treatment in the study provided that serum total 25-hydroxyvitamin D is ≥ 30 ng/mL. The washout period is not necessary if serum total 25-hydroxyvitamin D is <30 ng/mL.
9. If taking any bone modifying treatment that could interfere with study endpoints, must discontinue use of such agent(s) for the duration of the study.

10. Willing and able to comply with study instructions and commit to all clinic visits for the duration of the study.

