5.6 Method of Assigning Subjects to Treatment Groups

After signing the ICF, prior to any study-related activities, subjects will be assigned a site-generated, ascending subject identification number and will retain that number throughout the study. Should a subject be withdrawn from the study, the subject identification number will not be reassigned. Approximately 350 subjects will be screened to enroll approximately 108 subjects who meet the enrollment criteria.

An IRS will provide study treatment group assignments for these 108 subjects using the computer-generated randomization code provided by the IRS vendor. The randomization code will be stratified age group (8 to <12 years and 12 to <18 years) and balanced within each age group for gender and CKD stage (stages 3 and 4).

In Cohort 1 (ages 12 to <18 years), approximately 72 subjects, balanced for gender and CKD stage, will be randomized in a 2:1 ratio to active or placebo treatment, respectively. Ten (10) subjects will be randomly selected from the active group and five (5) subjects will be randomly selected from the placebo group for intensive PK evaluation during the last 3 days of the 12th week of treatment (prior to dose escalation). Twenty other subjects will be randomly selected for end of study PK evaluations from the active group, ten of which will be receiving an end of study dose of 30 mcg/day and the other ten will receiving an end of study dose of 60 mcg/day.

In Cohort 2 (ages 8 to <12 years), approximately 36 subjects, balanced for gender and CKD stage, will be randomized in a 2:1 ratio to active or placebo treatment, respectively. Ten (10) subjects will be randomly selected from the active group and five (5) subjects will be randomly selected from the placebo group for intensive PK evaluation during the last 3 days of the 12th week of treatment (prior to dose escalation). End of study PK evaluations will be made after 26 weeks of treatment. Twenty other subjects will be randomly selected for end of study PK evaluations from the active group, ten of which will be receiving an end of study dose of 30 mcg/day and the other ten will receiving an end of study dose of 60 mcg/day.

For both cohorts, an IRS will provide study treatment group assignments using the computer-generated randomization code.

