APPENDIX 1 SCHEDULE OF EVENTS

Schedule of Events	Screening Period			Treatment Period							
	Visit 1		Visit 2 ^a	Visit 3	Visit 4 ^b	Visit 5 ^b	Visit 6 ^b	Visit 7 ^b	Visit 8 ^b	Visit 9 ^b	Visit 10 ^b
			Randomized								
	Days -70 to -63	Days -62 to -8	Days -7 to -1	Day 1	Day 8	Day 15	Day 22	Day 29	Day 43	Day 57	Day 71
Sign ICF	1										
Review or confirmation of inclusion/exclusion criteria	1		1	1							
Medical history and demographics	1										
Prior/concomitant medications	1		1	1	1	1	1	1	1	1	1
Adverse events	1		1	1	1	1	1	1	1	1	1
Physical exam (including weight, height and BMI)	1			1							
VS measurements	1		1	1	1	1	1	1	1	1	1
12-lead ECG			1								
Urine pregnancy test, as needed ^c	1		1								
Clinical chemistry (full panel)	1 ^d		1								
Hematology	1		1								
Clinical chemistry (partial panel)			1	1	1	1	1	1	1	1	1
Urine chemistry	1		1								
Urinalysis			1								
Calculate eGFR	1		1								
Dispense study drug			1								
Drug accountability											
Plasma iPTH	1		1	1	1	1	1	1	1	1	1
Serum total 25D	1		1	1	1	1	1	1	1	1	1
Serum 25D3 [REDACTED]			1								
[REDACTED]			1								
Patient reported palatability and acceptability											

a. If washout of vitamin D, calcium and/or bone metabolism therapy is not required, Visit 2 is not required.
b. May occur \pm 3 days of scheduled day
c. Only for females of childbearing potential
d. Visit 1 creatinine value will be used to calculate screening eGFR
e. Additional blood draws required at -2, 2, 4 and 8 hours only if subject is participating in the intensive PK assessment
f. Visit required only if subject underwent dose titration at Visit 13
g. Visit required only for subjects participating in the second PK assessment

Schedule of Events	Treatment Period								
	Visit 11 ^e	Visit 12	Visit 13	Visit 14 ^{b,f}	Visit 15 ^b	Visit 16 ^{b,f}	Visit 17 ^b	Visit 18 ^b	Visit 19 ^b
Day 83 (-2 ^e , 0, 2 ^e , 4 ^e , 6, 8 ^e , and 12 hours)									
Sign ICF									
Review or confirmation of inclusion/exclusion criteria									
Medical history and demographics									
Prior/concomitant medications	1	1	1	1	1	1	1	1	1
Adverse events	1	1	1	1	1	1	1	1	1
Physical exam (including weight, height and BMI)									
VS measurements	1	1	1	1	1	1	1	1	1
12-lead ECG									
Urine pregnancy test, as needed ^c			1						
Clinical chemistry (full panel)			1						
Hematology			1						
Clinical chemistry (partial panel)	7	1		1	1	1	1	1	1
Urine chemistry			1						
Urinalysis			1						
Calculate eGFR									

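### Screening eGFR for subjects aged 8 to <18 uses the MDRD equation, which ignores body size, so the 15 to <60 entry window can wrongly exclude children, mainly boys and those aged 8 to <12; the source of CKD stage is also unstated

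*Combined protocol and SAP*

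**What the plan says.** Table 1 (Section 6.3) defines eGFR in two sentences: "This is a derived variable based in the Modification of Diet in Renal Disease equation", and "Visit 1 creatinine value to be used for eGFR calculation". Appendix 1, footnote d, repeats that the Visit 1 creatinine is used for screening eGFR. No section names a paediatric equation, yet Section 4.1 states: "The target population for this study is subjects having ages of 8 to <18 years". Table 1 also provides the input that MDRD lacks: "Height will be recorded to the nearest 1 cm at visits 1, 3 and 28/ET".

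Inclusion 2 (Section 4.2) requires a stage 3 to 4 diagnosis "at least six months prior to the screening visit, and have an eGFR of" 15 to <60 mL/min/1.73m². Both parts must be met.

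CKD stage is used in three further places:

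- Inclusion 4a sets the iPTH entry threshold by stage: "Plasma iPTH >100 pg/mL (stage 3 CKD) or >160 pg/mL (stage 4 CKD").
- Section 5.6 requires the randomisation code to be "balanced within each age group for gender and CKD stage (stages 3 and 4").
- Section 5.4 has stage-specific iPTH criteria for reducing and resuming dosing.

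Section 1.2 defines stages 3 and 4 purely by eGFR range (30 to <60 and 15 to <30). Section 4.1 refers to medical history and eGFR together, and Section 9.6 collects stage on the CKD history page. Nothing says which source feeds the interactive response system (IRS).

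**The concern.** MDRD takes creatinine, age and sex. A small child has less muscle and produces less creatinine, so a given creatinine should point to a lower GFR than in a nearly grown adolescent. MDRD does not see body size, and its age term moves the result the other way.

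An eGFR that reads too high acts first at the upper limit of inclusion 2. A child whose height-based estimate falls in stage 3 can compute at 60 or above and fail screening. The error depends on age and sex. It would fall hardest on Cohort 2, which has only about 36 places, and it would waste part of the roughly 350 screenings foreseen in Section 5.6. If the same value sets CKD stage, it also reaches the iPTH entry threshold and the balancing factor.

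**Working it through.** The plan gives no eGFR coefficient or misclassification rate, so there is no figure to reproduce.

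**Assumptions, none of them in the documents**

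- MDRD = 175 × Scr^-1.154 × age^-0.203, × 0.742 if female, race term omitted. A leading constant of 186 instead of 175 raises every value by 6% (186/175 = 1.063).
- Comparator = k × height (cm)/Scr, with k from 0.413 to 0.55.
- Typical heights: 125 cm at 8 years, 135 at 10, 148 at 12, 170 at 17.

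**Step 1: age effect at equal creatinine.** (8/17)^-0.203 = 1.17. An 8-year-old scores about 17% higher than a 17-year-old of the same sex. Height does not enter.

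**Step 2: single cases (boys).** For Scr 1.5 mg/dL, 1.5^-1.154 = 0.626.

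- Age 8, 125 cm, Scr 1.5: MDRD = 175 × 0.6263 × 0.6557 = 71.9, ineligible. Height-based: 0.413 × 125/1.5 = 34.4, or 0.55 × 125/1.5 = 45.8. Both are in the window.
- Age 10, 135 cm, Scr 1.5: MDRD 69, ineligible. Height-based 37 (k = 0.413) or 49.5 (k = 0.55). Both are in the window.
- Age 8, Scr 2.5: MDRD 39.9 (stage 3). Height-based 20.6 or 27.5, both stage 4.
- Age 8, Scr 2.0: MDRD 51.6 (stage 3). Height-based 25.8 (stage 4) at k = 0.413 but 34.4 (stage 3) at k = 0.55, so this disagreement depends on k.
- Age 8, Scr 4.0: MDRD 23.2, eligible. Height-based 12.9 (below 15) or 17.2 (in the window).

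**Step 3: where the upper limit falls.** The table gives the height-based value at the creatinine for which MDRD equals 60.

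| Subject | Scr | k = 0.413 | k = 0.55 |
|---|---|---|---|
| Boy, 8 y, 125 cm | 1.75 | 29.4 | 39.2 |
| Boy, 12 y, 148 cm | 1.63 | 37.4 | 49.8 |
| Boy, 17 y, 170 cm | 1.54 | 45.7 | 60.9 |
| Girl, 17 y, 170 cm | 1.19 | 59.2 | 78.8 |

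For the 8-year-old boy, the upper limit removes essentially all of height-based stage 3 at k = 0.413, and everything above about 39 at k = 0.55. For the 17-year-old girl the gap nearly vanishes at k = 0.413 and reverses at k = 0.55.

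**Step 4: shares by simulation.** Ages 8 to 18, both sexes, height-based value spread evenly over 15 to 60; creatinine back-calculated from height and MDRD then applied.

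| k | MDRD ≥60, all | MDRD ≥60, ages 8 to <12 | Stage 4 labelled 3, all | Stage 4 labelled 3, ages 8 to <12 |
|---|---|---|---|---|
| 0.413 | 35% | 49% | 39% | 60% |
| 0.45 | 27% | 41% | 29% | 48% |
| 0.50 | 18% | 31% | 17% | 32% |
| 0.55 | 11% | 21% | 9% | 20% |

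At ages 12 to <18 the share at 60 or above runs from 25% (k = 0.413) to 4% (k = 0.55). At k = 0.413 it is about 47% of boys and 21% of girls. The opposite relabelling, stage 3 to stage 4, runs from about 1% to 13%.

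Weighting the two age groups by the planned 72:36 cohort split gives (2/3 × 25) + (1/3 × 49) = 33% at k = 0.413 and (2/3 × 4) + (1/3 × 21) = 10% at k = 0.55.

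**The case against.** The case for leaving the plan alone has real content.

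**The sizes rest on constants that the plan does not give.** The share at 60 or above changes three-fold across the k range and the stage 4 relabelling about four-fold. The comparator is itself a creatinine estimate, not measured GFR. This stands: the results are disagreement with a height-based estimate, and no single percentage should be quoted alone. But even at k = 0.55 about one in five children aged 8 to <12 computes at 60 or above.

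**Stage.** A reader might infer that CKD stage is misassigned as a matter of fact, and with it the entry threshold, the balancing and the Section 5.4 criteria. The documents do not support that. Section 1.2 ties stage to eGFR, but Sections 4.1 and 9.6 also point to the history, and Sections 5.4 and 5.6 name no source. The stage effects are conditional. The eligibility effect is not, because a prior diagnosis cannot rescue a child who computes at 60 or above.

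**Who is affected.** A reader might take it that every subject is affected, or that MDRD rewards small size. Neither holds. MDRD is indifferent to size; the rise comes from age, and the error arises because size is left out. Two-thirds of the planned subjects are in Cohort 1, where the error is smaller.

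**Bias.** A reader might also infer a biased treatment comparison. The screening eGFR precedes randomisation and does not depend on arm. The primary endpoint (Section 9.8.1) is each subject's own iPTH change, and Section 9.10.1 does not name CKD stage as a stratum of the Cochran-Mantel-Haenszel test. Nothing here favours an arm or inflates the type I error.

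**Conclusion.** The point holds for the equation and for eligibility. The protocol applies an equation without a body-size term to a wholly paediatric population, and inclusion 2 depends on the result. On the stated assumptions, it would exclude about 35% (k = 0.413) to 11% (k = 0.55) of children whose height-based eGFR is 15 to 60, and 49% to 21% of those aged 8 to <12. The direction is firm for younger children and boys; in older adolescent girls the error is small or reversed. The size depends on k, the assumed heights and the even spread of GFR.

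Relabelling of stage 4 as stage 3 (about 39% to 9%) and of stage 3 as stage 4 (about 1% to 13%) applies only if stage is read from this eGFR. The plan should settle that question in any case. What is at risk is the population enrolled and how its stage is described, not the validity of the comparison between arms.

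**What to change.** - **Table 1:** replace MDRD with a validated paediatric height-and-creatinine equation suited to the central laboratory's creatinine assay. Write out the formula, use Visit 1 height and Visit 1 creatinine, and apply it to inclusion 2.
- **Source of stage:** state whether the CKD stage used for inclusion 4a and for IRS balancing comes from this value or from the CKD history.
- **Consistency:** reconcile Sections 1.2, 4.1, 4.2, 5.4, 5.6 and 9.6 and Table 1 on the source of stage. The stage referred to in Section 5.4 needs the same clarification; which clinical rule applies there is for the sponsor and its clinical advisers.
- **Subjects already randomised:** recompute eGFR from stored height and creatinine for the baseline description and stage-specific summaries. Leave treatment assignments as they are.

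The cost is a short amendment and a change to the laboratory and IRS calculation, with no new visit, sample or measurement. The downside is that some enrolled subjects may change stage, or fall outside 15 to <60, on recalculation. The report should say how many.
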